2.2 Study Objectives

2.2.1 Primary Objective(s)

The following primary objectives will be evaluated:

- To evaluate safety of COVID-HIG administered IM or SC as a single dose
- To evaluate PK of COVID-HIG administered IM or SC as a single dose

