Any anomalous concentration values observed prior to the first dose will be identified. Such values less than 5% of the observed C_{max} for the affected PK profile will be set to 0 (zero) for the calculation of PK parameters. The original concentration values will be used in statistical summaries. If the pre-dose value is greater than 5% of C_{max} , the affected PK profile will be excluded from statistical summaries and analysis. Similarly, PK concentrations for the affected profile will be excluded from statistical summaries.

Pharmacokinetic analyses will be performed separately for each administration route for the PK population, using the results of the binding IgG antibody assay (see Section 0). Comparative bioavailability will be presented between administration routes (IM to IV; SC to IV; and IM to SC), if data permit. Derived PK parameters, including both primary and secondary PK endpoints, will be tabulated by administration route for the PK population. Binding IgG SARS-CoV-2 antibody serum concentrations versus time curves will be summarized and plotted by administration route for the PK population.

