### 2.3.1 Methods of Randomization

Cohorts 1 and 2 (n=12 and n=24 but truncated to n=11, respectively) were randomized separately to receive a single dose of COVID-HIG via IM, SC, or IV. Randomization was stratified by SARS-CoV-2 detectable antibody status ( $\geq 15$ , but  $\leq 80$  AU/mL on the Diasorin LIAISON SARS-CoV-2 S1/S2 IgG antibody assay) and undetectable antibody ( $< 15$  AU/mL) at screening; subjects with antibody  $> 80$  AU/mL were excluded from the study as screen failures. The randomization was blocked in groups of 3 subjects assigned one each to the 3 treatment groups, so while the overall numbers of antibody-positive and antibody-negative subjects were not prespecified for Cohort 1, the site was instructed to complete all four blocks of three subjects. After enrollment of Cohort 1 was finished, enrollment caps were to be set for Cohort 2 to control the overall numbers of antibody-positive and antibody-negative subjects enrolled to be approximately equal; 18 or 21 antibody-positive subjects of 36 total subjects was permissible. Once randomized, subjects were not replaced even if not dosed.

Anti-SARS-CoV-2 Immunoglobulin Intravenous (Human) (NP-028), abbreviated as COVID-HIG  
EBS-CVH-006 Statistical Analysis Plan

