## **3 STUDY ENDPOINTS**

### **3.1 Pharmacokinetic Endpoints**

#### **3.1.1 Primary Pharmacokinetic Endpoints**

The following primary PK endpoints, based on PK sample test results of an immunobinding IgG assay and a pseudovirus neutralization assay, were to be evaluated in healthy adults. However, Protocol Amendment 3.0 removed the pseudovirus neutralization assay PK analysis due to low sensitivity of this assay, so only the immunobinding IgG assay PK endpoints were analyzed:

- $AUC_{0-\text{inf}}$ :  $AUC_{0-\text{last}}$  plus the additional area extrapolated to infinity after dosing
- $AUC_{0-\text{last}}$ : area under the concentration-time curve from time 0 to the last quantifiable concentration after dosing
- $C_{\text{max}}$ : maximum observed concentration after dosing
- $T_{\text{max}}$ : time at which  $C_{\text{max}}$  occurs after dosing
- $C_{28d}$ : observed or estimated concentration at Day 29 (28 days after dosing)

Anti-SARS-CoV-2 Immunoglobulin Intravenous (Human) (NP-028), abbreviated as COVID-HIG  
EBS-CVH-006 Statistical Analysis Plan

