#### **8.4.2 Pre-dose Concentration Values and Endogenous Compounds**

The study drug SARS-CoV-2 binding IgG antibody is not expected to exist in the serum prior to receiving any dose, because a negative rapid SARS-CoV-2 IgG/IgM antibody and antigen test results were required for inclusion. A pre-dose serum sample for SARS-CoV-2 antibody was drawn on Day 1. Any anomalous concentration values observed prior to the first dose are identified and are set to 0 (zero) for the calculation of PK parameters. The original concentration values are used in statistical summaries. If the pre-dose value is greater than 5% of  $C_{max}$ , the affected PK profile is excluded from statistical summaries and analysis. Similarly, PK concentrations for the affected profile are excluded from statistical summaries. If necessary, background subtraction may be applied for PK analysis.

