#### 8.4.6 Pharmacokinetic Analysis

All PK analyses are conducted based the PK population. All PK data listings are presented based on the PK population. A detailed listing for the excluded subjects is provided with reasons for exclusion.

PK concentration data are summarized by study day/nominal time point and treatment arm. The summary statistics for concentration data include n, arithmetic mean, SD, median, minimum, maximum, geometric mean and 95% CI, and percentage coefficient of variation (%CV).

PK parameters in [Table 3](#) are summarized by treatment arm overall and by baseline seronegative or seropositive SARS-CoV-2 antibody stratum. Summary of  $t_{max}$  includes n, median, minimum, and maximum only. For the other PK parameters, summary statistics include n, arithmetic mean, SD, median, minimum, maximum, geometric mean and 95% CI, and geometric percentage coefficient of variation (%CV). The geometric %CV is calculated as,

$$\%GCV(x) = 100 \times \sqrt{\exp(Var(\ln x)) - 1}$$

Scatterplots for individual PK concentration-time profiles are presented on linear and semi-logarithmic scales for the PK population. Mean and 95% CI concentration-time plots on linear and semi-logarithmic scales are presented by treatment arm overall and by baseline seronegative or seropositive SARS-CoV-2 antibody stratum.

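### The pre-dose exclusion limit is 5% of the participant's own Cmax, so retention in the PK analysis depends on a primary endpoint and bears on the antibody-positive stratum the trial plans to report

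*SAP*

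**What the plan says.** The SAP sentence (8.4.2) begins "If the pre-dose value is greater than 5% of" Cmax, and its consequence is that "the affected PK profile is excluded from statistical summaries and analysis". Protocol 9.4.2 agrees: "the affected PK profile will be excluded from statistical summaries and analysis". Both are worded as mandatory. Below the limit, the protocol says that a pre-dose value "for the affected PK profile will be set to 0 (zero) for the calculation of PK parameters". The SAP zeroes any anomalous pre-dose value, without that threshold.

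Cmax is the "maximum observed concentration after dosing" (SAP 3.1.1) and a primary PK endpoint. The primary PK objective is "To evaluate PK of COVID-HIG administered IM or SC as a single dose" (protocol 2.2.1). All arms get the same dose: the cohorts "were randomized separately to receive a single dose of COVID-HIG via IM, SC, or IV" (SAP 2.3.1).

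Pre-dose antibody is present by design. Protocol 4.2 excludes Diasorin IgG only above 80 AU/mL. Protocol 6.1 requires negative rapid IgM and antigen tests, not negative IgG. SAP 2.3.1 stratifies on antibody status and allowed 18 or 21 antibody-positive participants of 36. SAP 8.4.6 has the PK parameters "summarized by treatment arm overall and by baseline seronegative or seropositive SARS-CoV-2 antibody stratum". Yet SAP 8.4.2 says that antibody is not expected before dosing, on the ground that negative IgG and IgM results were required.

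Both documents allow baseline or background subtraction if necessary. Neither gives a trigger, or says whether subtraction comes before the 5% check.

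**The concern.** An exclusion rule should use only information that treatment cannot change. This one compares a baseline value with a post-dose primary outcome. Two participants with the same pre-dose antibody can be treated differently because one absorbed less. The IM and SC summaries then describe people whose exposure came out relatively high.

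If IM and SC peaks are lower than IV peaks at equal dose, the rule also removes antibody-positive profiles more readily in the two arms that carry the primary objective. The balance on antibody status that stratified randomization was meant to give is then lost among retained profiles, and SAP 6.6 plans no adjustment for that status. With 7-8 participants per arm, losing even one or two profiles unequally matters, and the seropositive summary could be left thin or empty.

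**Working it through.** The plan gives no figure for this rule, so there is none to reproduce. The dose arithmetic is consistent: 8.5 mL x 29,282 AU/mL = 248,897 AU, against about 250,000 AU stated.

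**Inputs from the documents.** 5% limit (SAP 8.4.2, protocol 9.4.2); assay LLOQ 1 and ULOQ 48 AU/mL (SAP 8.4.1); IV half-life about 24 to 30 days (protocol 2.1); 7-8 per arm (SAP 4); follow-up 56 days.

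**Step 1, the rule in algebra.** Let B be the pre-dose level and d the rise due to the dose, with observed Cmax = B + d. Exclusion occurs when B > 0.05(B + d), so 0.95B > 0.05d, so B > d/19. A baseline of 1 AU/mL needs Cmax of at least 1/0.05 = 20 AU/mL. At Cmax 48 the limit is 0.05 x 48 = 2.4 AU/mL. At a fixed B, the profiles with the smallest d are removed first, whatever the route.

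**Step 2, the route effect (inference).** With one compartment and first-order absorption at equal dose, the ratio of IM/SC to IV rise is F x exp(-ln2 x Tmax / half-life). F of 0.6-1.0 and Tmax of 2-7 days are assumed.
- Lowest: 0.6 x exp(-0.693 x 7/24) = 0.49.
- Highest: 1.0 x exp(-0.693 x 2/30) = 0.955.

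The ratio is below 1 in every combination tried. The protocol samples Days 3 and 6 only in the IM and SC arms, which fits a later peak but gives no size for it.

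**Step 3, tolerated baseline (d/19).** Two IV rises are assumed: 48 AU/mL, and 83 AU/mL (250,000 AU in an assumed 3 L, ignoring the difference between the dose and PK assays).
- Rise 48: IV 48/19 = 2.53; IM/SC 1.24 to 2.41 AU/mL.
- Rise 83: IV 83/19 = 4.37; IM/SC 2.14 to 4.17 AU/mL.

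**Step 4, illustrative simulation of the seropositive stratum.** There were 400,000 profiles per route and 36 scenarios. Assumed: lognormal baseline with geometric mean 1.5, 3 or 6 AU/mL and geometric SD 2 (values below 1 treated as zero); CV 25% or 40%; log-scale correlation of Cmax and AUC 0.8 in every arm; Cmax ratio 0.5, 0.7 or 0.9 paired with F 0.7, 0.8 or 1.0. Results for baseline geometric mean 3 and CV 25%:

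| IV rise | Cmax ratio | Excluded, IV | Excluded, IM/SC | AUC ratio, true to retained | Cmax-rise inflation, IV / IM-SC |
|---|---|---|---|---|---|
| 48 | 0.5 | 59% | 88% | 0.70 to 0.725 | 8% / 13% |
| 48 | 0.7 | 59% | 76% | 0.80 to 0.818 | 8% / 11% |
| 48 | 0.9 | 59% | 65% | 1.00 to 1.008 | 8% / 9% |
| 83 | 0.5 | 31% | 67% | 0.70 to 0.728 | 4% / 10% |
| 83 | 0.7 | 30% | 49% | 0.80 to 0.816 | 4% / 7% |
| 83 | 0.9 | 31% | 36% | 1.00 to 1.005 | 4% / 5% |

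Over all 36 scenarios, exclusions ran from 7% to 88% in IV and 10% to 98% in IM/SC, and were higher in IM/SC every time. The geometric mean Cmax rise in retained profiles was inflated by 1-35% (IV) and 2-51% (IM/SC). The AUC ratio moved up by under 1% to about 11% (0.775/0.70). A second simulation, with biexponential IV disposition and IM/SC Cmax at 43-55% of IV, gave a route-ratio shift of -6% to +12%, so the sign is not settled.

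**Step 5, would a fixed AU/mL limit do instead?** Take baseline 2 AU/mL, constant for 56 days, with half-life 27 days and a peak at time zero. Drug AUC0-56d = d x (27/ln2) x (1 - 2^(-56/27)) = 29.7d. The endogenous area is 2 x 56 = 112.
- Observed Cmax 40: 112/(29.7 x 38 + 112) = 9% of the area.
- Observed Cmax 20: 112/(29.7 x 18 + 112) = 17%.

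A fixed limit without subtraction would leave unequal endogenous contamination by route.

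**The case against.** The strongest reply is that the remedy is already in the text. Protocol 9.4.2 permits subtraction of the mean pre-dose titer, and SAP 8.4.2 permits background subtraction in the same paragraph as the exclusion. If every profile were corrected before the check, the selection would largely disappear. That is true, but the exclusion is mandatory, subtraction is optional, and no order is given. A programmer following the text literally would exclude.

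Second, both passages open with anomalous values, and protocol 9.4.2 says elsewhere that participants with elevated baselines may be excluded. The rule may not have been meant for a planned stratum. This stands as ambiguity; the 5% sentence itself carries no such limit.

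Third, a relative limit has a merit: it bounds the endogenous share of Cmax equally in every arm. That is a reason to prefer subtraction over a fixed limit, not a reason to keep the exclusion.

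Fourth, if peaks in all arms were capped at the ULOQ, the limit would be 2.4 AU/mL everywhere. SAP 8.4.4 states that substitution for concentration summaries and plots, not for PK parameters, so the point is unresolved.

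Fifth, the study is descriptive and the route comparison is secondary. With about 4 antibody-positive participants per arm (assumed half of 7-8) and CV 25%, the log SD is 0.246. The 90% CI factor for a route ratio is then exp(1.943 x 0.246 x sqrt(2/4)) = 1.40 each way (t on 6 df). A shift of 10% is small beside that. This limits the harm to the ratio; it does not answer the loss of profiles or the upward bias in Cmax.

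**Conclusion.** The concern holds in a limited form. Selection on a primary endpoint follows from the rule by algebra, taking observed Cmax as baseline plus rise. The upward bias in retained-profile Cmax follows if baseline is unrelated to the rise. That the limit is lower in IM/SC is a pharmacokinetic inference about arms on average, not about every pair of participants; the assumed Cmax ratio of about 0.5 to 0.95 puts the IM/SC limit about 5% to 50% below the IV limit. The effect on the route AUC ratio is probably about 10% or less, direction uncertain.

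Three stronger readings are tempting and are not supported:
- **That a stated share of antibody-positive IM/SC profiles will be lost.** The documents give no Cmax by route and no baseline distribution in the PK assay. The simulated percentages are scenarios.
- **That the Diasorin limits can be put straight into the rule.** Pre-dose values of 15 to 80 AU/mL would need Cmax of 300 to 1,600 AU/mL, which would suggest that the whole stratum disappears. No conversion from Diasorin units to PK-assay units is given.
- **That the route comparison is materially biased in a known direction.** The calculations give a modest shift whose sign depends on the kinetic assumptions.

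**What to change.** In SAP 8.4.2 and protocol 9.4.2:
- Make subtraction of the participant's own mean pre-dose value (Day -1 and Day 1) the rule for every profile with quantifiable pre-dose antibody, in place of the 5%-of-Cmax exclusion.
- Do not follow it by setting the pre-dose value alone to zero. Zeroing that one point leaves the endogenous level in every later concentration, and so in Cmax and AUC.
- Delete the SAP statement that antibody is not expected before dosing.
- Report the set left by the 5% rule as a sensitivity analysis, with numbers excluded by route and antibody stratum. SAP 8.1 and 8.4.6 already provide for exclusion reasons and listings, so the stratum split is the main addition.

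Do not substitute a fixed AU/mL limit without subtraction.

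The cost is wording in two documents and one further PK run. Both pre-dose samples are already scheduled, so no new data are needed. The downside is the assumption that endogenous antibody stays roughly constant over 56 days, which the report should state.

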#### **8.4.3 Exclusion of Outliers**

Individual serum concentrations may be excluded from the analysis because they are erroneous or abnormal at the discretion of the study statistician following a review of available documentation (e.g., bioanalytical report, validation report). Any such exclusion will be clearly listed in the study report along with justification for exclusion.

Entire serum concentration-time profiles for a participant may be excluded following review of available documentation (e.g., bioanalytical report, validation report, and protocol deviation log) as determined by the study statistician. Any such exclusion will be clearly listed in the study report along with justification for exclusion.

Any excluded data is flagged in the individual data listings.

#### **8.4.4 Non-quantifiable and Missing Concentrations**

When calculating summary statistics, including geometric mean and 90% CIs and PK parameters, PK (SARS-CoV-2 antibody) concentrations below the assay's LLOQ are imputed as

Anti-SARS-CoV-2 Immunoglobulin Intravenous (Human) (NP-028), abbreviated as COVID-HIG  
EBS-CVH-006 Statistical Analysis Plan

half of the LLOQ value. If the lower bound of the CIs is below the LLOQ, it will be replaced by “<LLOQ” in the output.

If a concentration value is below the LLOQ:

- Individual concentration listings in the CSR list these concentrations as “<LLOQ.”
- For the calculation of concentration summaries and plotting mean and individual concentration-time profiles, concentration values <LLOQ are treated as LLOQ/2 and values above the ULOQ are substituted with ULOQ.

For the purpose of calculating PK parameters:

- Missing pre-dose concentrations and concentrations prior to the first quantifiable concentration that are <LLOQ are set to 0 (zero).
- A value of <LLOQ after  $C_{max}$  that is between two quantifiable data points is treated as missing.
- Values of <LLOQ after the last quantifiable concentration value at the end of the collection interval are set to 0 (zero).
- For calculation of  $\lambda_z$  and parameters that depend on  $\lambda_z$ , trailing zero values are treated as missing.
- If there are more than two consecutive values <LLOQ after  $C_{max}$ , all subsequent values may be treated as missing, or the <LLOQ values themselves may be treated as missing, after review of available documentation (e.g., bioanalytical report, validation report).
- Missing concentration values are ignored in the calculations.

#### 8.4.5 Pharmacokinetic Parameters

PK parameters in [Table 3](#) will be derived from the concentration-time data by non-compartmental analysis (NCA; i.e., log-linear trapezoidal) methods using actual sampling times; concentrations at nominal time points may be imputed using linear interpolation. If the actual sampling time is missing, but a valid concentration value has been measured, the nominal time as specified in the protocol may be used. Additional partial AUCs may be added as needed. For partial AUCs through a given time point, the partial AUC will be set to missing unless an actual time point occurs within  $\pm 10\%$  of the nominal timepoint for a given profile.

Bioavailability will be compared between administration routes, if data permit. An analysis of variance (ANOVA) model will be used with  $AUC_{0-inf}$  as the dependent variable and administration route as the fixed effect. The adjusted least square means will be used to estimate ratios of  $AUC_{0-inf\text{ IM}} / AUC_{0-inf\text{ IV}} * 100\%$ ,  $AUC_{0-inf\text{ SC}} / AUC_{0-inf\text{ IV}} * 100\%$ , and  $AUC_{0-inf\text{ IM}} / AUC_{0-inf\text{ SC}} * 100\%$  along with corresponding two-sided 90% CIs calculated based on the ANOVA. The width of the 90% CIs will be examined relative to the standard of [80%, 125%] for comparative bioavailability. If the area extrapolated from the time of the last measured concentration to infinity is greater than 40% of the total AUC for a subject profile, then the observation will be excluded from bioavailability analyses. No adjustment for multiplicity will be applied, and no formal hypothesis testing will be performed.

Anti-SARS-CoV-2 Immunoglobulin Intravenous (Human) (NP-028), abbreviated as COVID-HIG  
EBS-CVH-006 Statistical Analysis Plan

NCA PK parameter calculations and graphics are performed using SAS version 9.4 or higher.

$\lambda_z$	Apparent first order terminal elimination rate constant. It is calculated by linear regression analysis of log concentration values that include consecutive data points in the terminal phase (i.e., including the last quantifiable value, preferably not including C max ) that maximizes the adjusted $r^2$ . A minimum of 3 data points is required for determination. If the maximum adjusted $r^2$ is <0.700, it is considered not estimable and the $\lambda_z$ will not be included in statistical analyses.
t 1/2	Terminal elimination half-life, or just referred to as half-life. It is calculated as $((\ln 2)/\lambda_z)$ , when $\lambda_z$ can be estimated.
CL	Apparent systemic clearance. It is calculated as (dose / AUC 0-∞ ). Note that the dose needs be measured by the same PK assay and expressed in the same unit.
V z	Apparent volume of distribution (during the terminal phase). It is calculated as (CL / $\lambda_z$ ).

Anti-SARS-CoV-2 Immunoglobulin Intravenous (Human) (NP-028), abbreviated as COVID-HIG  
EBS-CVH-006 Statistical Analysis Plan

#### 8.4.6 Pharmacokinetic Analysis

All PK analyses are conducted based the PK population. All PK data listings are presented based on the PK population. A detailed listing for the excluded subjects is provided with reasons for exclusion.

PK concentration data are summarized by study day/nominal time point and treatment arm. The summary statistics for concentration data include n, arithmetic mean, SD, median, minimum, maximum, geometric mean and 95% CI, and percentage coefficient of variation (%CV).

PK parameters in [Table 3](#) are summarized by treatment arm overall and by baseline seronegative or seropositive SARS-CoV-2 antibody stratum. Summary of  $t_{max}$  includes n, median, minimum, and maximum only. For the other PK parameters, summary statistics include n, arithmetic mean, SD, median, minimum, maximum, geometric mean and 95% CI, and geometric percentage coefficient of variation (%CV). The geometric %CV is calculated as,

$$\%GCV(x) = 100 \times \sqrt{\exp(Var(\ln x)) - 1}$$

Scatterplots for individual PK concentration-time profiles are presented on linear and semi-logarithmic scales for the PK population. Mean and 95% CI concentration-time plots on linear and semi-logarithmic scales are presented by treatment arm overall and by baseline seronegative or seropositive SARS-CoV-2 antibody stratum.

#### 8.5 Exploratory Efficacy Endpoint

For subjects that become SARS-CoV-2 positive during the study period (at any time post-dosing on Day 1 and up to last follow-up visit/contact) an Ordinal Outcome Scale is collected to assess COVID-19 symptom severity. Maximum score on the Ordinal Outcome Scale is summarized by treatment arm and overall and presented in a subject listing for the SARS-CoV-2 Positive population with data available.

